analytical methods	
 
* Description of transmission dynamics: rolling incidence rate of COVID-19 disease throughout one year, adjusting for the sensitivity of SARS-CoV-2 RT-PCR on nasal swabs by delay between symptom onset and testing; SARS-CoV-2 infection incidence rate, SARS-CoV-2 annual attack rate, secondary infection rate, and infection fatality risk by age group, by adjusting for the proportion asymptomatics.
 
* Risk factor analysis for SARS-CoV-2 infection and COVID-19 disease, and for severity (hospitalisation), overall and following household transmission in particular.
 
* Model basic and effective reproductive numbers (<math>R_0</math> and <math>R_e</math>), generation time distribution, ratio of transmissibility between symptomatic and asymptomatic cases, duration of the infectious period, household secondary infection rate.
 
* Explore the correlation between <math>R_0</math> and <math>R_e</math>, and the uptake of measures to reduce exposure/ transmission.
 
* Case-cohort, case- control or similar analysis to estimate vaccine effectiveness against confirmed COVID-19 in the population-based surveillance and cohort analysis to estimate vaccine effectiveness against SARS-CoV-2 seroconversion (among sero-survey participants)
 

safety	
The study does not involve an investigational product or intervention

statistical methods	Descriptive (probabilistic) and inferential statistics Negative binomial regression for risk factor analysis Development of a compartmental mathematical model to describe the spread of SARS-CoV-2 on the population level
---------------------	---

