### 3. Study Design

Prospective cohort study (observational). We will use the established HDSS to set up population-based COVID-19 surveillance in a household cohort. From any individual in this population reporting any respiratory sign (symptom or lowered peripheral oxygen saturation) or loss of smell or taste, with or without fever, we will collect a respiratory specimen and test these for SARS-CoV-2 virus by PCR, during 12 months. These cases will be identified through bi-weekly household visits, through an alert system involving community leaders and HDSS interviewers, or when presenting with symptoms at healthcare centres or at the referral hospital. Identified healthcare facilities will then alert the study team if a possible case from the HDSS population is consulted or admitted, if the patient agrees. Demographic, epidemiological and clinical data (comorbidities, medication, obesity, HIV, TB, smoking) of possible cases and of the source population will be recorded at baseline; recent illness, potential risk exposure of each household member (including duration and type) to SARS-CoV-2 positive individuals, uptake of measures to reduce exposure/transmission, and barriers to the uptake of such measures, will be

recorded/updated during every household visit. COVID-19 vaccination status will be recorded from possible cases and compared to that of a subset of the population, in a case-cohort design to determine vaccine effectiveness against symptomatic COVID-19.

An age-stratified serial sero-survey will be conducted at baseline in a subset of the population in the population-based COVID-19 surveillance, and at 3, 6 and 12 months, after confirmation of community transmission. Recording vaccination status of all sero-survey participants, we will determine vaccine effectiveness against SARS-CoV-2 seroconversion in a cohort design.

Household transmission will be specifically investigated, by investigating contact history, vaccination status, and the presence of SARS-CoV-2 virus and serology among household members twice during the month after the symptom onset of a household index case.

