### 4.2 Selection and recruitment

All households in the HDSS (2108 during the last round in 2019) consenting to participate in the study will be **visited biweekly** by a trained HDSS interviewer, following the same procedures as in routine HDSS rounds, specified in the HDSS protocol (Instituto Nacional de Saude, 2016). We assume the same number of households will consent to participate as in other HDSS rounds. Based on previous experience with the HDSS, we expect the HDSS interviewer to visit 6 households per working day on average.

Household heads, or an adult delegated by the household head, will be asked about COVID-19 consistent symptoms among any consented household member, using a structured questionnaire. If a household member is identified by the household head as reporting any respiratory sign (symptom or lowered peripheral oxygen saturation) or loss of smell or taste, with or without fever, in the last week, i.e. a possible COVID-19 case, this household member will be asked to consent for participating, to respond to a structured questionnaire and to collect a nasal swab sample for SARS-CoV-2 testing. Specimens will be tested for SARS-CoV-2, using RT-PCR (at INS in Marracuene). Possible COVID-19 cases in the HDSS households will be detected through four entry points:

- Biweekly HH visits
- Phone call by patient (when symptoms occur)
- Phone call by study team (as currently done in HDSS)
- HDSS household members presenting as COVID-19 suspected case in healthcare facility

If meeting the COVID-19 admission criteria as per national guidance, the possible COVID-19 case will be referred to the Polana Caniço General Hospital (PCGH), the closest healthcare facility and COVID-19 patient management centre.

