### 5. Study Procedures

#### 5.1 Study/visit schedule

Table 2. Schedule of assessments for population-based surveillance. One row corresponds to two weeks.

we ek	month	Informed consent (1)	Sero- survey	Household visit (2)	Unscheduled visit for swab collection	Case Follow- up outcome (3)	Social mixing & uptake (4)
1	Oct20	x	x	x		x	
3				x	x	x	
5	nov/20			x	x	x	x
7				x	x	x	
9				x	x	x	

11	dec/20			x	x	x	
13			x	x	x	x	
15	jan/21			x	x	x	
17				x	x	x	x
19	feb/21			x	x	x	
21				x	x	x	
23	mar21			x	x	x	
25			x	x	x	x	x
27	apr/21			x	x	x	
29				x	x	x	
31	may21			x	x	x	
33				x	x	x	
35				x	x	x	
37	jun/21			x	x	x	
39				x	x	x	
41	jul/21			x	x	x	
43				x	x	x	
45	aug/21			x	x	x	
47				x	x	x	
49	sep/21			x	x	x	x
51			x	x	x	x	
53						x	
55						x	
TOTAL forms filled*		2800 for household surveillance,2400 for sero-survey,8000 for swab collection	2400*4= 9600	2800*5= 70000	8000	8000	2400*4= 9600
TOTAL samples*			2400*4= 9600		8000		

Type of sample		DBS for serology, collected at home**		nasal swab for PCR, collected at home**		
----------------	--	---------------------------------------	--	---	--	--

DBS = dried blood spot

1 Informed consent for household surveillance (by the household head) and sero-survey (by the selected individual or their caretaker) during baseline visit

2 During baseline visit adapted questionnaire to update population characteristics

3 Only of COVID-19 confirmed cases identified by the surveillance, at 28 and 56 days after symptom onset

4 We plan the social mixing survey rounds each time one month after the sero-survey, to spread the workload. The same participants from the sero-survey are asked to complete the questionnaire

\* estimated, based on the available information at the start of the study; we anticipate 8000 respiratory episodes (possible cases), based on previous data from the HDSS, adjusted for increased frequency of reporting (previous data was recorded during three-monthly rounds)

\*\* both serology testing of DBS and PCR testing of nasal swabs will be carried out at INS Marracuene. DBS samples are collected during pre planned visits, PCR samples when a possible case is identified. Nasal swabs undergo PCR testing the day following sample collection and results are communicated back to the individual (or his/her caretaker) that same day.

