All HDSS households will be visited by a trained HDSS interviewer to present the study and ask for informed consent (i) by the household head for the population-based surveillance and (ii) by the individuals selected for the age-stratified serial sero-survey. During this same visit, if the household head consented, the demographics data (baseline household visit form) will be verified and updated. A study household card with unique IDs of each household member will be provided (code containing the housing block, household id and sequential household member number). Household members will be sensitized on symptoms related to COVID-19, are asked to keep track of possible symptoms they may develop, and inform the study team by phone if a household member has a respiratory symptom, loss of smell or taste, so that upon assessment he/she can be asked to be swabbed for virological testing. In case a household member presents with symptoms which classify him/her as a possible case, a separate individual informed consent procedure for nasal swabbing will have to be performed prior to sampling. This ICF covers sampling for the first episode and any subsequent episode during the study period when nasal sampling would be indicated. Also during the baseline household visit, if full informed consent was provided (both for surveillance by the household head and for the sero- and social mixing survey by the individual household member), individual household members selected for the sero-survey will be asked for a baseline dried blood spot sample on filter paper, by administering a few blood drops through a finger prick.

Every two weeks a trained interviewer from the HDSS team will do calls to the head of the household or his representative, where during the call he will fill out a questionnaire (Household follow-up visit form) recording any respiratory symptoms, fever or other indicative sign of COVID-19 (at the time of the phone call, or in the last two weeks, if these symptoms go away), vaccination against COVID-19, and medical appointments that any family member has had.

Meanwhile (if applicable), demographic changes or changes in the chronic medical conditions of family members will be recorded. If a family member reports a respiratory sign or loss of smell or taste, with or without fever (possible case), a trained interviewer will do a home visit to this household.

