We will derive brand-specific total vaccine effectiveness against infection and against disease, in respectively a case-cohort design and a cohort design. Total vaccine effectiveness is the protection of vaccinees due to direct effects and added protection of vaccinees owing to vaccination of their neighbors or contacts, while overall vaccine effectiveness considers protection of an entire population, irrespective of the vaccination status of its individual members, due to the combination of total protection and protection of non-vaccinees due to vaccination of their neighbors or contacts (Ali et al 2015). To derive total vaccine effectiveness against infection, we will compare the proportion of sero-survey participants who seroconverted in the past 3 months among vaccinated against the proportion in non-vaccinated, adjusting for age and sex and other confounders. To derive total vaccine effectiveness against disease, we will compare the odds of vaccination among symptomatic confirmed SARS-CoV-2 cases detected through the population-based surveillance with the odds of vaccination among sero-survey participants who did not seroconvert in the past 3 months, in a case-cohort design. We will also explore overall vaccine effectiveness against disease using regression models comparing housing blocks with different levels of vaccination coverage among sero-survey participants.

We will estimate the conventional data-based secondary attack rate, which is the proportion of seroconversion among identified household contacts. However, these are not necessarily all secondary infections from the household index case, and could be tertiary. Therefore we will also derive a model-based secondary attack rate, estimating the number of actual secondary infections of the household index case. To do so, we could use a chain-binomial statistical model, as described by Jing et al (doi:10.1016/S1473-3099(20)30471-0), with an expectation-maximisation algorithm to account for (a) uncertainty in the infection time of asymptomatic infections, for (b) an incubation and infectious period distribution, as described in literature, and consider (c) the timing of symptom onset in

symptomatic household contacts and (d) the age-specific proportion of asymptomatic infections as estimated from the active population-based surveillance and sero-survey.

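### Vaccine effectiveness against disease compares people who had to be reported and swabbed with people who did not; a test-negative contrast should be prespecified beside it

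*Combined protocol and SAP*

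**What the plan says.** The Synopsis leaves the design open: "Case-cohort, case- control or similar analysis to estimate vaccine effectiveness against confirmed COVID-19 in the population-based surveillance". Section 3 narrows it to a case-cohort design: "COVID-19 vaccination status will be recorded from possible cases and compared to that of a subset of the population". Section 7.1 specifies the two groups. The case side is "the odds of vaccination among symptomatic confirmed SARS-CoV-2 cases detected through the population-based surveillance"; the comparison side is "the odds of vaccination among sero-survey participants who did not seroconvert in the past 3 months, in a case-cohort design".

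The two groups enter by different routes.

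- **Cases.** Section 4.2 lists four entry points: household visits, calls by the patient, calls by the study team, and attendance at a health facility. At the household contact, a person becomes a possible case "If a household member is identified by the household head as reporting any respiratory sign" (or loss of smell or taste). Section 5.1 then requires that "a separate individual informed consent procedure for nasal swabbing will have to be performed prior to sampling". The PCR must also be positive.
- **Comparators.** Section 4.2 draws the sero-survey as a simple random sample within each age stratum, regardless of disease history. These people pass only the sero-survey consent, for which section 5.2 anticipates 10% refusal.

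Section 7.1 states adjustment for age, sex and other confounders for effectiveness against infection. It states none for effectiveness against disease, and nothing addresses reporting or swab acceptance by vaccination status. Vaccination status is recorded for possible cases (Synopsis, section 3), so it is available for those who test negative. Section 7.1 does not use them for this purpose.

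**The concern.** Any difference by vaccination status in being reported or in accepting a swab changes the case group and leaves the comparators untouched. It therefore multiplies the odds ratio directly. Adjusting for age and sex would not remove it.

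The protocol itself makes such a difference plausible. The Synopsis names distrust and income loss among the barriers to measures that include future vaccination, and section 10.6 says that the stigma of home testing in protective equipment is unknown. The same attitudes could influence vaccination, symptom reporting and swab consent.

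Brand-specific effectiveness against PCR-confirmed clinical infection is a listed secondary objective. As planned, the study could not tell a vaccine effect from a difference in ascertainment.

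**Working it through.** **Inputs.** Section 7.2: 40% attack rate, 50% symptomatic, 90% identified, 2,790 cases, 20% coverage, VE 50%. Table 1: 15,393 people, 2,400 sero-survey participants, and 1-in-10 testing above 50 confirmed cases a week. Table 2 footnote: 8,000 possible cases. Assumed, because the documents give no value: k, and PCR sensitivity of 70-80%.

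**The plan's own figure.** 15,393 × 0.40 × 0.50 × 0.90 = 2,771, against 2,790 stated. A population of 15,500 gives 2,790 exactly. The difference is immaterial. No sample size or power is stated for effectiveness against disease.

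**Bias of the planned contrast.** Let k be the probability of being reported and swabbed for a vaccinated COVID-19 case, divided by that for an unvaccinated one. Then observed VE = 1 - (1 - VE) × k.

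| k (assumed) | True VE 50% reads | True VE 0% reads |
|---|---|---|
| 0.6 | 70% | 40% |
| 0.8 | 60% | 20% |
| 1.0 | 50% | 0% |
| 1.25 | 37.5% | -25% |

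**Which k fit 90% overall ascertainment?** Take 20% coverage and read the 90% as covering both reporting and swabbing.

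- True VE 0%: vaccinated people are 20% of cases. For k = 0.8, unvaccinated ascertainment is 0.90 / (0.8 + 0.2 × 0.8) = 93.75% and vaccinated is 75%. Feasible.
- True VE 50%: vaccinated people are 0.1 / 0.9 = 11.1% of cases. For k = 0.8, unvaccinated ascertainment is 0.90 / (0.889 + 0.111 × 0.8) = 92.0% and vaccinated is 73.6%. Feasible.
- Upper limit at true VE 50%: if every vaccinated case is found, unvaccinated ascertainment is (0.90 - 0.111) / 0.889 = 88.75%. So k is at most 1 / 0.8875 = 1.13, and VE reads 1 - 0.5 × 1.13 = about 44%.
- k = 1.25 at true VE 50% allows overall ascertainment of at most 0.111 + 0.889 / 1.25 = 82%; k = 1.5 allows at most 0.111 + 0.889 / 1.5 = 70%.

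**Test-negative contrast.** With k defined separately for the two kinds of illness, observed VE = 1 - (1 - VE) × k(COVID) / k(non-COVID).

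- Equal k: reads 50% and 0%, the true values, with a perfect PCR.
- k(COVID) 0.6 and k(non-COVID) 0.8, for example because vaccinated COVID-19 cases are milder: 1 - 0.5 × 0.75 = 62.5% at true 50%, and 25% at true 0%. The planned contrast reads 70% and 40%.
- k(COVID) 0.8 and k(non-COVID) 1: both contrasts read 60% at true 50%.
- False-negative PCR puts cases among the controls. Per person, take a COVID-19 episode rate of 0.18 in the unvaccinated and 0.09 in the vaccinated, and a non-COVID rate of 5,210 / 15,393 = 0.338. At 80% sensitivity the odds ratio is 0.5 × (0.338 + 0.036) / (0.338 + 0.018) = 0.525, so VE reads 47.5%. At 70% it reads 46.3%.

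**Precision** (crude 95% CI at VE 50% and 20% coverage; 8,000 - 2,790 = 5,210 taken as an illustrative number of test-negatives):

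| Testing | Cases | Sero-survey comparators (2,400) | Test-negatives |
|---|---|---|---|
| All possible cases | 2,790 | 42-57% | 43-56% (5,210) |
| 1 in 10 throughout | 279 | 26-66% | 23-68% (521) |

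Expected cases average 2,790 / 52 = 53.7 a week, so the 1-in-10 rule could apply for part of the year.

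**The case against.** A random sample from an enumerated population is a legitimate case-cohort comparator, and ascertainment here does not rest mainly on spontaneous care-seeking. Section 5.1 has every consenting household contacted every two weeks whatever its vaccination status, with a visit if it cannot be reached by phone and in-person visits every three months. One respondent answers for the whole household. This limits how far k can lie from 1. It stands as mitigation, but it does not show that k equals 1: the 90% is an overall assumption, and swab consent is still individual.

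A reader might infer that effectiveness could be badly understated, at 37.5% or 25%. At true VE 50% those readings need overall ascertainment of at most 82% or 70%, so section 7.2's assumptions would have to fail.

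A reader might also infer that test-negative controls are plentiful because 5,210 are expected. The 8,000 comes from earlier HDSS data and the 2,790 from an assumed attack rate, and nothing shows that one contains the other. Both cover the whole study, including time before vaccine rollout, which section 1.1 describes as only planned. Under 1-in-10 testing the test-negatives thin out and the sero-survey comparators do not.

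Finally, the Synopsis wording already permits a case-control analysis. That is so, but section 7.1 does not take it up.

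**Conclusion.** The concern holds as a design bias of unknown size in a secondary objective; no stated figure is wrong because of it. A reporting or swabbing ratio other than 1 passes directly into the planned odds ratio, and nothing in section 7.1 would detect it. At k = 0.8, which the plan's own 90% ascertainment allows, effectiveness is overstated by 10 points at true VE 50% and by 20 points at true VE 0%. Understatement at true VE 50% is limited to about 6 points (reading about 44%) while the 90% and 20% assumptions hold. Every value of k is assumed.

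A reader might infer that test-negative controls would remove the bias and should replace the planned contrast. The documents do not support this. The controls cancel k only if it is the same for COVID-19 and other respiratory illness, and they add an assumption that vaccination does not affect other respiratory illness. The supportable conclusion is narrower: a second contrast with different weaknesses, on data already collected, would reduce the bias and make differential ascertainment visible.

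**What to change.** In section 7.1, keep the case-cohort contrast. Prespecify beside it a test-negative contrast: vaccination odds, with status taken at symptom onset, in PCR-positive against PCR-negative possible cases whose onset falls after vaccine introduction, adjusted for onset week, age, sex and entry route. Report both with their assumptions. Treat divergence as a sign of differential ascertainment. Divergence will not show which estimate is right, and agreement does not exclude bias, as the example with k(COVID) 0.8 and k(non-COVID) 1 shows.

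The cost is SAP wording and one regression on collected data, provided that the forms allow vaccination status at onset to be established. The downsides to state are:

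- It assumes that vaccination changes reporting equally for COVID-19 and other respiratory illness, and does not affect the risk of the latter.
- False-negative PCR lowers VE by about 2.5 to 4 points at 80% to 70% sensitivity.
- Under 1-in-10 testing throughout, its interval is slightly wider: about 23-68% against 26-66%.

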# 1. Introduction

## 1.1 Background

In sub-Saharan Africa, official Covid-19 case numbers are an underestimate because of limited surveillance and testing capacity, whereby testing, when it happens, is not systematic and focuses on high probability suspects, either severe, imported cases or their contacts. This provides a very limited and biased assessment of transmission and burden in the population and hence public health impact, also hampering implementation of targeted interventions (Ahmed A, 2020). Furthermore, comorbidities (such as HIV or TB) and malnutrition are more common in sub-Saharan Africa and are likely to affect disease dynamics and outcomes. Despite concerns of a possible pending catastrophic impact of Covid-19 on Africa, there is also still a pervasive hope that perhaps younger populations in warmer, humid tropical Africa, living mainly outdoors, might be less affected, which has been postulated as an explanation as to why months after the initial reported clusters of cases, so far still no or limited widespread transmission has been reported in many sub-Saharan African countries (Casanova et al 2020; Notari A 2020).

Nevertheless, experience from other enveloped respiratory RNA viruses such as influenza virus shows that respiratory transmission can occur throughout the year in tropical Africa with occasional usually erratic peaks (Gessner et al 2011). In Maputo, Mozambique, slightly south of the Tropic of Capricorn, influenza transmission is more seasonal once again, though in most years, two peaks can be observed (Nguenha et al 2018). Despite unclear seasonality in much of Africa, age-stratified estimates of mortality rate of the 2009 pandemic influenza were as high if not higher as elsewhere globally (Dawood et al 2011). Similarly, archival studies have estimated a huge societal impact of the 1918 influenza pandemic on the health of African populations (Andayi F 2019). Moreover, epidemiologic studies on endemic human coronaviruses in Kenya have shown substantial year-round circulation (Munywoki et al 2018). This suggests that SARS-CoV-2 could have a high impact in Africa, although SARS-CoV-2 is different in key ways to influenza virus and to other coronaviruses. Data from higher income country contexts is poorly applicable to African settings. Some lower resourced southern hemisphere settings have already seen large increases in cases in early April, such as Ecuador, but in the Southern temperate region, we only started to observe high intensity transmission from the end of May onwards.

Several demographic, cultural and environmental factors may affect the transmission of SARS-CoV-2 in communities and within households in Africa. These include population density, population age structure, poor-quality housing (including exposure to indoor smoke), climate, different intensity and pattern of contact (e.g. between the ages), different distribution of co-morbidities, different exposures to vaccines and infections, but also the ability to adhere to interventions aimed at interrupting transmission, such as physical distancing (including quarantine and isolation), use of masks and of water/soap for hand-washing. In addition, host factors may affect transmission. For instance, HIV-infected persons with low CD4 counts may shed longer as is the case with influenza (von Mollendorf et al 2018), and there may be differences in ACE2 receptors (the binding receptor for SARS-CoV-2) densities across populations (Cao et al 2020) or other genetic factors (Ellinghaus et al preprint 2020). Host factors and co-morbidities more prevalent or specific to Africa could also affect to what extent an individual presents with asymptomatic or clinical illness, which may also affect transmissibility and infectiousness (Cohen et al 2015).

Knowledge about transmission parameters will allow for the design of targeted, specific control measures to interrupt spread of SARS-CoV-2 through behaviour modification, social distancing and use of personal protective measures. In addition, intensity of transmission and prevalence of risk groups for infection and disease translates to population level burden of disease and the incidence rate of that

burden in communities. Understanding the number of events of relative severity, size of risk groups for severe disease and the current and projected rate of change of disease is critical to plan for current and future capacity for health care.

The transmission potential of SARS-CoV-2 is determined in any particular context by the basic reproduction number ( $R_0$ ) when there is no protective immunity in the population.  $R_0$  will vary with time and context, such as population density, number of contacts and environmental conditions, and is dependent on the period of infectiousness, viral load, and the serial interval. Early data estimated the  $R_0$  for SARS-CoV-2 between 2.0 and 3.4 (Ferretti 2020; Li 2020), higher than that for seasonal influenza (Biggerstaff et al 2014). This is likely in part because of key divergent features from influenza such as pre and asymptomatic SARS-CoV-2 transmission (Ferretti 2020; Kimball 2020; He 2020), near absence of severe disease in young children (Wu et al 2020), and a longer estimated serial interval of 3.96 days (Du Z Emerging Infect Dis 2020). The SARS-CoV-2 average  $R_0$  is also higher than estimated for previous novel viruses, such as influenza H1N1 in the 1918 ( $R_0=1.8$ ) and 2009 ( $R_0=1.6$ ) pandemics (Biggerstaff et al 2014) and SARS-CoV-1 ( $R_0=1-5$ ) (Liu et al 2020).

To date, evidence suggests that in temperate climates between 20 and 50% of infections could be asymptomatic (Mizumoto et al 2020; Bi et al 2020; Kimball et al 2020). Pre-symptomatic shedding is common, with comparable viral load in asymptomatic, pre-symptomatic and clinical cases (Kimball et al 2020). This complicates timely targeted application of interventions since people may not know they are infected and will not behave as if they were. The frequency of asymptomatic infection in sub-Saharan African settings is as of yet unclear, and also may vary by setting. Understanding the proportion of asymptomatic infections and their contribution to the reproduction number is important.

Immune factors may affect community transmission. Cross reactivity with existing endemic coronaviruses, (CoVs 229E, NL63, HKU1,OC43), two of which are related beta-coronaviruses (HKU1,OC43), could result in protection from infection and/or disease. Many models assume a person can no longer be infected once recovered (Fig 1). However, immunity to coronaviruses is unclear. Antibody titer to SARS-CoV-1 infection waned over a period of several months in recovered patients (Liu et al 2006), but unclear if this means waning protection. Additionally, endemic human coronaviruses existing neutralising antibodies may not sufficiently protect against reinfection (Callow et al 1985), while some reports of reinfection with SARS-CoV-2 have been reported, though none fully documented.

[figure not shown]

Fig 1. Susceptible-Infected-Recovered Model

In the first few weeks of 2021, vaccines under WHO's Emergency Use Listing have begun to be used in several countries and plans exist to roll out one or more vaccine types in Mozambique. Vaccine effectiveness studies are key to better understand how these vaccines perform in different settings, especially since the emergence of SARS-CoV-2 variants circulating in Mozambique against which several current vaccines may not protect.

